5.1 Drug Administration Training

All subjects and study partners will receive extensive training at each visit regarding home administration of IN insulin using the SipNose during visits 1 and 2 (screening and baseline, respectively). Subjects will be required to administer the dose twice daily; once in the morning and again in the evening (at least 8 hours between doses). Subjects will have the opportunity to immediately do a retrial administration if they are unsuccessful in releasing the study drug intranasally. If the SipNose device is discharged prior to insertion into the nose, then a retrial admission would be indicated. However, if the device is discharged following nasal insertion, then a retrial would not be permitted. The steps to ensure that subjects maintain compliance with the study protocol over 3 weeks include administering the following during the study:

- In-clinic training session during screening and baseline visits
- Phone calls to assess compliance from study coordinator at weeks 1 and 2 (approximately 1 and 2 weeks after baseline visit)

In addition to drug administration training, subjects will be given a daily Drug Diary to record the time and date of each self-administered dose, drug vial number and any comments for study staff. Instructions and training for the Drug Diary will be given to all subjects and study partners at the same times as the drug administration training.

5.2 Drug Administration with SipNose

REDACTED

5.3 Device Dose Loading and Administration

REDACTED

5.4 Study Duration

Study participation will last approximately 8 weeks, consisting of a screening visit, baseline visit, a follow-up assessment visit and three phone visits. Patients who discontinue treatment will continue follow-up measures as possible and will be analyzed as randomized per the intent to treat principal.

6 Study Population

6.1 Eligibility Criteria

6.1.1 Inclusion Criteria

1. Subject who has Idiopathic PD defined by the cardinal sign, bradykinesia, plus the presence of at least 1 of the following: resting tremor or rigidity and without any other known or suspected cause of Parkinsonism (according to MDS clinical diagnostic criteria for Parkinson's disease- Postuma et al, Movement Disorders 2015), confirmed by a fellowship trained movements disorder specialist
2. Subject who is Hoehn & Yahr stage less than or equal to 3
3. Subject has a MOCA score ≥ 16 .
4. Subject is >40 and <90 years of age.
5. Female subjects who are post-menopausal or have a negative pregnancy test
6. The subject must be proficient in speaking, reading and understanding English in order to comply with procedural testing of cognitive function, memory and physiology.
7. Subject has provided informed written consent prior to participation. In the event that subject is legally unable to provide informed written consent due to deterioration in cognitive abilities, fully informed written consent must be provided by a legally authorized representative.
8. Subject is on a stable dose (at least 1 month prior to baseline visit) of antiparkinsonian agents and is willing to remain on this dose for the duration of the study. If the subject is on a cholinesterase inhibitor, a stable dose without changes for 1 month is also required.
9. Subject must have undergone a brain CT or MRI prior to the study as part of their previous diagnostic workup for PD to rule out underlying structural lesions, as determined clinically significant by the investigator

6.1.2 Exclusion Criteria

A subject will not be included for consideration in this study if any of the following criteria are met:

1. Subject who has atypical Parkinson's syndrome(s) due to drugs (e.g., metoclopramide, neuroleptics), metabolic neurogenetic disorders (e.g., Wilson's Disease), encephalitis, cerebrovascular disease, or degenerative disease (e.g., progressive Supranuclear Palsy, Multiple system atrophy, corticobasal degeneration, Lewy Body dementia)
2. Subject has medical history and/or clinically determined disorders: chronic sinusitis, untreated thyroid disease, or significant head trauma.
3. Subject has history of any of the following: moderate to severe pulmonary disease, poorly controlled congestive heart failure, significant cardiovascular and/or cerebrovascular events within previous 6 months, condition known to affect absorption, distribution, metabolism, or excretion of drugs such as any hepatic, renal or gastrointestinal disease or any other clinically relevant abnormality that inclusion would pose a safety risk to the subject as determined by investigator.
4. Subject has had previous nasal and/or oto-pharyngeal surgery and severe deviated septum and/or other anomalies.
5. Subject has history of any psychiatric illness that would pose a safety risk to the subject as determined by investigator.
6. Subject is currently taking sedative medications that are clinically contraindicated as determined by investigator.
7. Subject has undergone a recent change (<1 month) in their anti-parkinsonian medication, cholinesterase inhibitor or anti-depressant medication.
8. Subject has current or recent drug or alcohol abuse or dependence as defined by DSM-IV TR.
9. Screening laboratory results that are medically relevant, in which inclusion would pose a safety risk to the subject as determined by investigator.
10. The subject has participated in a clinical trial investigation within 3 months of this study.
11. The subject has an insulin allergy.
12. The subject has Insulin-dependent diabetes

7 Study Assessments and Procedures

A summary of study events and procedures is outlined in the Study Visit Table. Demographic, Screening, and Baseline Assessments are described in Sections 7.1.1-7.1.2, the Treatment Phase is outlined in Sections 7.1.2-7.1.5, and the Safety monitoring are detailed in Section 7.3; details of neuropsychological assessments are outlined in Section 7.5.

The diagnosis of Parkinson's disease will be confirmed by exam or chart review by a movement disorders neurologist prior to study enrollment. A recent office visit (within 3 months) may be used to replace a portion of the screening visit if information needed for determining eligibility is present within the electronic medical record. Upon confirmation of eligibility, subject returns for assessments and procedures as described below.

7.1 Demographic and Baseline Assessments

7.1.1 Visit 1: Screening

The following procedures will be performed at this visit:

- Obtain written informed consent from study partner and subject (or subject's legally authorized representative) prior to any study related procedures.
- Administer MoCA

- Review Inclusion/Exclusion Criteria.
- Review medical history, as it pertains to inclusion/exclusion criteria, such as research diagnosis, disease severity, and course of PD
- Obtain subject's demographic information (date of birth, gender, race, education, etc.).
- Obtain details of medications taken over the course of the last 30 days
- Complete physical exam, including neurological exam with UPDRS part III. Collect vital signs, height and weight prior to ECG and blood draw.
- Obtain laboratory studies
- Perform a standard 12-lead ECG.
- Study Drug administration training, including Study Drug Diary Training
- Hypoglycemia rescue training
- Visit 2 will be scheduled within 2 weeks (\pm 5 days).

7.1.2 Visit 2: Baseline/Initial Treatment Visit (Week 0)-fasting

The following procedures will be performed at this visit:

- Review Inclusion/Exclusion Criteria.
- Collect vital signs, orthostatic vital signs and weight.
- Collect concomitant medication information and record AEs/SAEs.
- Neuropsychological testing, including scales for mood, apathy and suicidality assessment (7.5)
- Perform UPDRS III
- Obtain laboratory studies, blood draw and glucose finger sticks
- Study Drug administration training (following cognitive testing).
- Hypoglycemia rescue training.
- Randomization of subject
- Administer first intranasal dose in clinic and provide study kit
- Visit 3 will be scheduled in 21 days (\pm 5 days).

7.1.3 Phone Visit 1: Safety Check (week 1)

- Study staff phone call to address AEs/SAEs 1 week (\pm 5 days) after visit 2

7.1.4 Phone Visit 2: Safety Check (week 2)

- Study staff phone call to address AEs/SAEs 2 weeks (\pm 5 days) after visit 2

7.1.5 Visit 3: Final Treatment and Safety Visit (week 3)-fasting

The following procedures will be performed at this visit:

- Collect vital signs, orthostatic vital signs and weight.
- Collect concomitant medication information and record AEs/SAEs.
- Collect administration supplies, study diary, and remaining study drug
- Physical and neurological examination
- Neuropsychological testing, including scales for mood, apathy and suicidality assessment (7.5)
- Administer MoCA
- Perform UPDRS III

- Obtain laboratory studies

See **Table 3** for specific list of laboratory assessments

7.1.6 Phone Visit 3: Safety Check (week 4)

- Study staff phone call 1 week (\pm 5 days) after visit 3 to follow up and address AEs/SAEs

7.2 Early Withdrawal

If subject withdraws from the study after the screening visit, but before initial study drug administration, no further evaluations are necessary. If subject withdraws from the study after initial study drug administration, all safety assessments will be performed (see section 7.3).

7.3 Safety

For all safety assessments described below, any clinically significant change will be recorded as an AE or SAE.

7.3.1 Physical Examination

Complete physical examination will be performed at visits 1 and 3, or if the subject withdraws or is withdrawn from the study early. Any abnormalities noted at Visit 1, will be documented as part of the subject's medical history.

7.3.2 Neurological Examination

Neurological examination will be performed at visits 1, 3 or if the subject withdraws early. Any abnormalities noted at Visit 1, will be documented as part of the subject's medical history.

7.3.3 Vital Signs

Vital signs will be recorded at all visits. Blood pressure and heart rate to be measured after subject has been sitting quietly for a minimum of 5 minutes. Diastolic blood pressure will be measured at the disappearance of Korotkoff sounds. Vitals sign will be monitored by clinical staff during each visit of the study. Orthostatic vital signs will be measured after patients have remained in the supine position for 5 minutes, and again after 2 minutes standing. We will collect three sets of orthostatic vital signs at baseline, at least 10 minutes apart, and use the average of these 3 measurements for comparison to a single measurement of post-treatment orthostatic vital signs (Visit 3).

A blood glucose < 70 mg/dL will be considered clinically significant. Patients will be given training regarding hypoglycemic rescue therapy and contacting 911 in severe cases. Any episodes will be reported to the study coordinator and research team. The likelihood of peripheral hypoglycemia is relatively low based on numerous clinical trials performed in the AD and healthy aging population showing no effects of IN insulin on peripheral glucose.

Vital signs will be taken prior to ECG and blood draw.

7.3.4 Weight

Body weight will be measured at all visits.

7.3.5 ECG

A standard 12-lead ECG will be performed on subjects at visit 1.

7.3.6 Laboratory Samples

At the screening visit, the laboratory samples will be drawn independent of fasting or non-fasting status.

At the baseline and final visit, all subjects will be required to fast for a minimum of 12 hours prior to collection of blood sampling on designated fasting visits.

At the baseline visit, the subject will receive the first intranasal dose in clinic. Once before the administration of the first dose (baseline) and twice after the administration of the first dose (approximately 15 minutes and 30 minutes after first dose), glucose finger sticks will be performed to measure blood sugar levels for patient safety.

See **Table 3** for specific list of laboratory assessments

7.4 PD Motor Assessment

The **United Parkinson's Disease Rating Scale (UPDRS)** is the most widely used clinical rating scale for Parkinson's disease. In this study, we only use part III of the rating scale, which is a clinician-scored monitored motor evaluation, allowing ratings from 0 (no symptoms) to 4 (severe symptoms) for each Parkinson's motor symptom. The Movement Disorders Society (MDS) commissioned a revision of the scale, resulting in a new version, termed the MDS sponsored UPDRS revision (MDS-UPDRS) (Goetz et al, 2008). In this study, the MDS-UPDRS version will be used.

7.5 Neuropsychological Assessment

The neuropsychological battery consists of subtests in a variety of domains that include working memory, visuospatial skills, processing speed, inhibition, set-shifting, verbal fluency, learning, memory, and mood.

7.5.1 Global Cognition:

7.5.1.1 *Montreal Cognitive Assessment*

The Montreal Cognitive Assessment (MoCA) is a brief cognitive screening measure that has been validated for use among individuals with Parkinson's disease. The total score for this test is 30 points, but one point will be added for individuals with ≤ 12 years of education, up to a maximum of 30 points. The cutoff point for normal cognition is 26/30 in the general population (Nasreddine et al., 2005) and in individuals with Parkinson's Disease (Hoops et al., 2009).

7.5.2 Working Memory:

7.5.2.1 *WAIS-IV Digit Span:*

The Digit Span task includes three different components: Digits Forward, Digits Backward, and Digit Sequencing (Wechsler, 2008). During Digits Forward, the participant is read a series of numbers and is asked to recall the numbers in the same order. Digits Backward requires the participant to recall the numbers in reverse order. Digit Sequencing requires the participant to recall the numbers in ascending order. During the first trial of each component, only 2 digits are read to the participant and the number of digits become gradually longer in length as the test continues.

7.5.3 Processing Speed and Set-Shifting

7.5.3.1 *Trailmaking Test Part A and B*

Trailmaking test is often used in research and clinical practice to assess processing speed, visual scanning, and mental flexibility (Heaton et al., 2004). Part A requires participants to connect a series of

dots in order from 1 to 25 as quickly as possible while maintaining accuracy. Part B requires participants to connect a series of dots with numbers and letters in ascending order by starting with a number and then connecting a line to the next letter, and back to the next number as quickly as possible. The task is timed and the number of errors are recorded.

7.5.4 Visuospatial Ability

7.5.4.1 *Judgement of Line Orientation*

Judgement of Line Orientation is a test of visual perception where participants are asked to estimate the angle between two line segments (Benton et al., 1978). There are 30 items and the participant earns one point for each response where they correctly identify both line segments for each item.

7.5.5 Learning and Memory

7.5.5.1 *Logical Memory*

Logical Memory is an auditory story-recall subtest from the Wechsler Memory Scale – Fourth Edition (Wechsler, 2009). Participants are read two short stories and are immediately asked to recall as much detail as they can remember. Following a 20-30 minute delay, they are asked again to recall details from the stories. Finally a forced-choice Yes/No recognition task will also be administered.

7.5.5.2 *Hopkins Verbal Learning Test- Revised*

The Hopkins Verbal Learning Test- Revised is a list-learning task which includes a list of 12 words (Brandt, 1991). There are 3 semantic categories within each list, meaning 4 of the words are semantically related. Standard test administration includes 3 learning trials where the entire list of 12 words is verbally presented to the participant and they are asked to repeat as many words as they can recall after each presentation. The test also includes a 20-25 minute delay where participants are then asked to recall the words previously learned. This is followed by a 24-word yes/no recognition task, which includes the 12 target words from the original list and 12 foils. Alternate forms will be used at different time points in the study to reduce the potential for practice effects.

7.5.5.3 *Brief Visuospatial Memory Test - Revised*

The Brief Visuospatial Memory Test- Revised is a visuospatial learning and memory task which includes 6 shapes displayed in an array (Benedict, 1997). Standard administration includes 3 learning trials where the participant is allowed to view the page with the 6 figures for 10 seconds and then they are asked to draw the shapes as accurately as they can in the correct location on the page. The test also includes a 20-25 minute delay where participants are then asked to recall the figures previously learned. This is followed by a 12 item yes-no recognition task, which includes the 6 figures they were initially exposed to and 6 foils. Alternate forms will be used at different time points in the study to reduce the potential for practice effects.

7.5.6 Inhibition

7.5.7 *Stroop Color and Word Test*

The Stroop Color and Word Test measures cognitive flexibility and inhibition of an overlearned or automatic response. During the first trial (Word), the examinee is asked to read the words green, blue, or red printed in black ink as quickly as they can. During the second trial (Color), there are XXXXs printed in green, blue, or red ink and the examinee is asked to and name the ink color as quickly as they can. The third trial (Color-Word) includes the words with the names of colors, but the ink does not match the print and the examinee is asked to report the color of the ink, inhibiting the response to read the word. For example, the word "red" is printed in green ink, and the correct response for the third trial is "green" (Golden and Freshwater, 2002). Each condition is 45 seconds in length.

7.5.7.1 *Letter Fluency*

For the phonemic fluency task, examinees are instructed to name as many words as they can that begin with a particular letter of the alphabet as quickly as they can (Heaton et al., 2004). Sixty seconds are allowed for each letter.

7.5.7.2 *Category Fluency*

For the category fluency task, examinees are asked to generate as many items that they can think of that belong to a particular category as quickly as possible in 60 seconds.

7.5.8 Mood

7.5.8.1 *Beck Depression Inventory- Second Edition*

This self-report measure is widely used in research and clinical practice to measure the presence and severity of depressive symptomatology (Beck et al., 1996). The measure consists of 21 items assessing symptoms of depression experienced within the previous two weeks. Each item contains four statements reflecting various degrees of symptom severity.

7.5.9 Apathy Scale

The examiner will ask the participant about the severity of a variety of symptoms of apathy experienced within the previous four weeks (Starkstein et al., 1992). The measure includes 14 items with 4-point Likert scale ratings. This measure was specifically designed for patients with Parkinson's disease and has been recommended for use in Parkinson's disease by the Movement Disorder Society Task Force on apathy and anhedonia (Leentjens et al., 2008).

7.5.10 Suicidality

Columbia Suicide Severity Rating Scale (C-SSRS)

The C-SSRS is a suicidal ideation rating scale to evaluate suicidality. It rates an individual's degree of suicidal ideation on a scale, ranging from "wish to be dead" to "active suicidal ideation with specific plan and intent" (Interian et al., 2018). The C-SSRS will be administered by trained raters at specified time points, as indicated in table 2 as well as when clinically indicated. Any subjects demonstrating evidence of suicidality will prompt immediate consultation with the site's on-call psychiatrist for assistance with decision-making and potential referral to behavioral health services.

Table 3: Schedule of Assessments

Assessment/ Procedure	Visit 1: Screen	Visit 2: Baseline/Initial Treatment (fasting)	Phone Visit 1: Safety Check after 1 week	Phone Visit 2: Safety check after 2 weeks	Visit 3: Final Treatment / Safety (fasting)	Phone Visit 3: Safety Check	Early Withdrawal
Schedule – Week and Windows	Week -2	Week 0	Week 1	Week 2	Week 3	Week 4	
		±5 days	±5 days	±5 days	±5 days	±5 days	
Informed consent	X						
Review of inclusion/exclusion criteria	X	X					
Medical History, demographic	X						
Physical/neurological exam	X				X		
UPDRS	X	X			X		
Vital signs	X	X			X		
Orthostatic vital signs		X			X		
Height	X						
Weight	X	X			X		X
12-lead ECG	X						
Basic Metabolic Panel (Na, K, CO2, CL, BUN, Creatinine, Glucose and Ca)	X				X		X
Glucose Finger Stick		X					
Fasting glucose		X			X		X
Insulin Level		X			X		X
HbA1c	X						
Thyroid Stimulating Hormone (TSH)	X						
Vitamin B12	X						
Pregnancy Test (in females)	X				X		X
Randomization		X					

Working Memory: WAIS-IV Digit Span		X			X		
Processing Speed and Set-Shifting Trailmaking Test Part A and B		X			X		
Visuospatial Ability Judgement of Line Orientation		X			X		
Learning and Memory Hopkins Verbal Learning Test- Revised		X			X		
Inhibition Stroop Color and Word Test		X			X		
Verbal Fluency Letter Fluency		X			X		
Verbal Fluency Category Fluency		X			X		
Mood Beck Depression Inventory- Second Edition		X			X		
Learning and Memory Brief Visuospatial Memory Test - Revised		X			X		
Learning and Memory Logical Memory		X			X		
Apathy Scale		X			X		
MoCA	X				X		
C-SSRS		X			X		X
Study Drug administration training	X	X					
Hypoglycemia rescue training	X	X					
Concomitant medications		X			X		
IN INSULIN compliance			X	X			
Adverse events		X	X	X	X	X	X

8 Investigational Product(s)

8.1 Description of Investigational Product

The research staff will utilize the following investigational products:

- Intranasal delivery route
- Regular insulin (Novolin-R; Insulin Full Prescribing Information)
- SipNose Device (Sections 2, 5.2, 5.3, and Investigator's brochure)

8.2 Handling and Storage

The study drug (insulin/saline) will be given to participant/care partner after training for administration.

The study drug will be kept at study site per label recommendations and institutional Standard Operational Policy, specifically, but not limited to temperature controlled secure area.

Participants will be instructed to keep unopened study drug according to label recommendations.

The study drug will be stored at room temperature. To ensure that a stable temperature and/or conditions are maintained, site staff will verify and document refrigerator temperature at a minimum of three times per week or monitored continuously if automated systems such as temp trak are used. An electronic log will be securely stored at the HealthPartners Neuroscience Center. Study staff will be responsible for safeguarding and maintaining the master log. In the event of a medical emergency

requiring a blind break, unblinded study staff will be contacted to relay the appropriate information only to those responsible for the patient's immediate medical care (e.g. ED physician).

8.3 Packaging and Labeling

Actual pharmacy-product indicator will be decided by unblinded staff in order to maintain investigator objectivity.

All study drug will be labeled according to the following specifications:

- Protocol identifier/IRB approval/account/study number
- Quantity statement
- Participant ID #
- "For Clinical Trial Use Only"
- Study contact # [contact]

8.4 Occupational Safety

No known significant safety risks exist to site personnel in direct or indirect contact with the study drug.

9 Concomitant Medications and Non-Drug Therapies

9.1 Permitted Medications

Any medication not listed in list of Prohibited Medications (see below) will be permitted during this study. A record will be kept by site staff detailing doses and indication of any concomitant medications used by subjects.

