In this study, we aim to investigate which intranasal insulin dose out of three doses and placebo, administered at three different doses or placebo over a 21-day period, is the optimum dosage based on safety and tolerability in Parkinson's disease. A similar design was used in a trial investigating intranasal oxytocin in frontotemporal dementia (Finger et al., 2014). Dosing for the first two groups of this study is based on previously conducted intranasal insulin studies in AD and MCI (Craft et al., 2012; Craft et al., 2017), using daily doses on 20 and 40 IU of intranasal insulin. Higher dose have been found to be safe in healthy adults (Benedict et al., 2007a). Prior studies performed have demonstrated favorable effects of this regimen in the MCI/AD population without peripheral hypoglycemia (Craft et al., 2012).

Furthermore, this clinical trial will investigate exploratory outcomes related to the effect of IN insulin on cognition, mood, apathy and motor performance measured by the MDS- UPDRS (United Parkinson's Disease Rating Scale, (Goetz et al., 2008)). To our knowledge, there are no published clinical trials investigating the use of IN insulin in PD.

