12.3 Statistical Analysis of Second Aim – efficacy measures

For each of the efficacy outcome measures, we will report mean differences and 95% confidence intervals between Visit 2 (Baseline/Initial Treatment) and Visit 3 (Final Treatment/Safety) for each study group. In the event of an early withdrawal, measures taken at the early withdrawal visit will be used in

place of Visit 3 data, if possible. Possible trends in cognitive function, motor function, and mood and apathy scores will be addressed.

We will look at the individual components and domains assessed by the chosen cognitive, motor, mood, and apathy measures to determine if any appear to be more sensitive to IN insulin. We will also explore the data for components that have a larger dose response. That is, they increase or decrease as the dose-level increases.

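### Cholinesterase inhibitors and antidepressants must be stable for a month before entry, but no rule keeps them stable between Visits 2 and 3, when change in cognition and mood is measured (minor, cheap to fix)

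*Combined protocol and SAP*

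**What the plan says.** Three places govern these drugs.

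- **Entry.** Exclusion 7 (section 6.1.2 and the Protocol Summary) rules out a candidate if "Subject has undergone a recent change (<1 month) in their anti-parkinsonian medication, cholinesterase inhibitor or anti-depressant medication". Inclusion 8 (section 6.1.1 and the Protocol Summary) adds, on cholinesterase inhibitors: "If the subject is on a cholinesterase inhibitor, a stable dose without changes for 1 month is also required". It does not mention antidepressants.
- **On study.** Inclusion 8 asks that the subject has been on a stable dose "of antiparkinsonian agents and is willing to remain on this dose for the duration of the study". That commitment is attached to antiparkinsonian agents only. Section 9.1 says: "Any medication not listed in list of Prohibited Medications (see below) will be permitted during this study". Section 9.2 names insulin use in insulin-dependent diabetes and several classes that can impair cognition, such as opiates and anticholinergics. The cognition clause is worded as a possible exclusion at screening. Cholinesterase inhibitors and antidepressants are not on the list, and anticholinergics are a different class.
- **Analysis.** Section 12.3 reports the mean difference from Visit 2 to Visit 3 with a 95% confidence interval in each group, and adds: "Possible trends in cognitive function, motor function, and mood and apathy scores will be addressed". Nothing in section 12 refers to medication changes during the study.

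The data exist. Section 9.1 has staff record doses and indications, and the procedures at Visits 2 and 3 include this item: "Collect concomitant medication information and record AEs/SAEs".

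**The concern.** The protocol itself treats a recent change in any of three drug classes as a reason not to enrol. For one class it carries that protection through to the final assessment. For the other two the protection stops at baseline. The Visit 2 scores are shielded from a recent change and the Visit 3 scores are not, although the quantity reported is the difference between them.

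Cognition, mood and apathy are secondary endpoints, and they are summarised in groups of 7 to 9 people. At that size one participant who starts or changes an antidepressant or a cholinesterase inhibitor can visibly move a group summary, up or down, for a reason unrelated to insulin. What is at stake is how the exploratory trends are read, not a test or a safety conclusion.

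**Working it through.** The plan states no power, effect size or standard deviation for these endpoints, so there is no figure of its own to reproduce. The check compares the rules and adds two short pieces of arithmetic.

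**1. Rule by drug class**

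| Class | Stable month before entry | Stable dose during study |
|---|---|---|
| Antiparkinsonian | Yes (inclusion 8, exclusion 7) | Yes (inclusion 8) |
| Cholinesterase inhibitor | Yes (inclusion 8, exclusion 7) | Not stated |
| Antidepressant | Yes (exclusion 7) | Not stated |

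For the last two classes, starting a drug on study is expressly allowed by 9.1. Stopping it or changing its dose is not addressed; it is open only because no rule forbids it. Eligibility is reviewed at Visits 1 and 2 but not at Visit 3 (Table 3).

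**2. Age of an on-study change at Visit 3**

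Section 7.1.2 says "Visit 3 will be scheduled in 21 days", with a window of 5 days either way.

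- Earliest: 21 − 5 = 16 days after Visit 2.
- Latest: 21 + 5 = 26 days after Visit 2.

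A change made after Visit 2 is therefore at most 26 days old at a Visit 3 held within its window. That is less than 1 month, the recency that exclusion 7 rules out at entry.

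The recall periods of two scales overlap this interval. The depression inventory covers the previous two weeks (7.5.8.1). As 14 < 16, at Visit 3 its recall period lies wholly after Visit 2. The Apathy Scale covers four weeks (7.5.9). As 28 > 26, its recall period spans the whole interval.

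**3. Weight of one participant**

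Group sizes are 7, 7, 9 and 7 (Table 2). If a medication change shifts one participant's score by X, the group's mean change moves by X/n:

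- n = 7: X/7 = 0.14X
- n = 9: X/9 = 0.11X

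The shift can go in either direction. The documents give neither X nor the proportion of participants likely to change these drugs, so the calculation stops here.

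**The case against.** The strongest case against has four parts.

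- **Section 9.1 is about which drugs are allowed, not about dose.** This stands. A reader might infer that 9.1 and 9.2 license stopping or adjusting these drugs. The text expressly permits only starting them; for the rest there is silence.
- **The cholinesterase-inhibitor sentence can be read more generously.** It follows directly on the commitment to stay on dose, says *also*, and does not tie its month to the baseline visit. A site might take it to continue during the study. This partly stands, so the gap is clearest for antidepressants, which inclusion 8 does not mention at all.
- **Randomisation and blinding deal with it.** They make a systematic difference between groups unlikely, and section 5.4 analyses participants as randomised. This stands against any claim of bias toward one dose. It does not remove chance imbalance in groups of 7 to 9, and 12.3 reports changes within groups. The confidence intervals will widen with the added noise, but they do not show its source.
- **The information would surface anyway.** A new or worsening symptom is an adverse event (11.1), and events are summarised by group (12.2). The clinical reason for a drug change would often appear there. The drug change itself would not be set beside the efficacy results, although it can be recovered from the recorded data.

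**Conclusion.** There is a real but small gap in on-study coverage; the criteria do not contradict each other. By its own entry rule the protocol regards a change less than 1 month old in these two classes as disqualifying, yet leaves such a change open during the 16 to 26 days over which cognition, mood and apathy are measured. The consequence is possible noise or chance imbalance in exploratory within-group summaries: X/7 or X/9 per participant affected.

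Two stronger readings should be resisted.

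- **Size.** A reader might want to express the shift in standard deviations, or as a share of a confidence interval. That needs a shift size and a rate of medication changes, and the documents supply neither. With three weeks of treatment the effect is probably small.
- **Dose.** A reader might infer that the choice of dose is at risk. Section 1.1.4 says the aim is to find which dose "is the optimum dosage based on safety and tolerability". Section 12.4 also mentions trends in the secondary outcomes, but gives no rule by which they would select a dose. Safety conclusions and dose choice are unaffected.

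**What to change.** Leave the antiparkinsonian sentence of inclusion 8 as it is. Replace its last sentence, in section 6.1.1 and in the Protocol Summary, with:

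*A subject taking a cholinesterase inhibitor or an antidepressant must have been on a stable dose for at least 1 month before baseline. All subjects, whether or not they take these drugs at entry, agree not to start, stop or change the dose of a cholinesterase inhibitor or antidepressant between Visit 2 and Visit 3 unless clinically necessary.*

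The second sentence binds non-users as well, so that new starts are covered.

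An optional companion in section 12.3 is to list any such changes between Visits 2 and 3 by study group, beside the as-randomised efficacy summaries, with no scores excluded. On its own this would be only a reporting detail. Next to the rule it shows the clinically necessary changes that the rule still allows.

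**Cost.** An eligibility criterion is amended in two places, and an elective change in these drugs waits about 3 weeks. No new data are needed, because concomitant medication is already collected at Visits 2 and 3, and every score stays in the analysis. The rule prevents only elective changes; clinically driven ones will still occur.
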